### 12.6.7 Pregnancy Testing

A serum pregnancy test will be performed in all women of childbearing potential at the Screening Visit. Urine pregnancy tests will be performed during the remainder of the study at the times indicated in the flow chart.

Individual pregnancy test results will be listed only.

## 12.7 Immunogenicity Analysis

The immunogenicity analyses will be performed first in the Immunogenicity Analysis Set and repeated in the Full Analysis Set if any subjects were excluded from the Immunogenicity Analysis Set.

### 12.7.1 Immunogenicity Variables

The primary immunological outcome variable is the number of PBMC producing IFN- $\gamma$  (ELISpot score) in response to exposure to the following 9 individual peptides (P877, P151, P113, P856(K), P753(K), P376, P797(K), P277(K) and P1266(K)) or a mix of the 9 peptides (LPMIX9), measured using 2 different assays: (1) an ex-vivo IFN $\gamma$  ELISpot and (2) a cultured IFN $\gamma$  ELISpot.

ELISpot scores will be constructed from the raw IFN- $\gamma$  ELISpot counts. Description of the algorithm used to calculate ELISpot score are presented for information only in [Appendix 2](#).

#### 12.7.1.1 Immune Response

Descriptive statistics (mean, SD, median, quartiles, minimum and maximum) will be generated by treatment group and time point for the following ELISpot score variables:

- ELISpot scores and change from Baseline for individual peptides and LPMIX9
- Sum ELISpot scores and change from baseline across the 9 individual long peptides

Sum ELISpot score is defined as the sum of the 9 ELISPOT scores from the 9 individual peptides.

In addition, standard errors and 95% CIs derived from a one-sample t-test will be presented for change from baseline.

Baseline is defined as the mean of the ELISpot scores prior to the first injection.

In addition, line plots of the mean ( $\pm$  SE) ELISPOT scores over time will be presented by treatment group for each individual peptide, LPMIX9 and the sum score of the 9 individual peptides for the cultured assay over the Immunogenicity Analysis Set. If the Full Analysis differs from the Immunogenicity Analysis Set, then the figures will be repeated for the Full Analysis Set.

Similarly, line plots of each individual patient's ELISPOT score over time will be presented, grouped by treatment group for each individual peptide, LPMIX9 and the sum score of the 9 individual peptides for the cultured assay over the Immunogenicity Analysis Set. If the Full Analysis differs from the Immunogenicity Analysis Set then the figures will be repeated for the Full Analysis Set.

### 12.7.2 Exploratory Immunogenicity Analyses

PRA Health Sciences and/or Altimmune may conduct exploratory analyses of the immunogenicity data.

Any exploratory analyses presented in the Clinical Study Report must be clearly described as 'exploratory'.

Descriptive statistics for observed values at a nominal visit as well as change from baseline values may be presented by cohort, country, and/or gender.

## 12.8 Virology Analysis

Blood samples will be collected for the assessment of virological parameters at the times indicated in **Table 1**.

Descriptive statistics for Virology parameters values:

- Quantitative Hepatitis B surface antigen (HBsAg) [presented in log10]
- Hepatitis B virus (HBV) DNA

and changes from baseline (in SI units) at each assessment time point will be presented by treatment group and visit for all subjects in the Immunogenicity Analysis Set and repeated for the Full Analysis Set if different.

Standard errors and 95% CIs derived from a one-sample t-test will be presented for change from baseline for HBsAg.

In addition, a line plot of the change from baseline in log10 HBsAg at each timepoint will be presented by treatment group.

The antibody to hepatitis B surface antigen (HBsAb) will be summarised by 'seroconverted' or 'not seroconverted' by visit for the Immunogenicity Analysis Set and repeated over the Full Analysis set if different. Seroconversion corresponds to HBsAb > 10 mIU/mL.

Individual subject results for all virology parameters will be listed for the Full Analysis Set.

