1. At estimated effective dose(s), and in the presence or absence of an estimated effective dose of a compatible adjuvant, is the vaccine safe and tolerated in nucleoside analogue (NA)-treated HBV patients with stable disease?
2. Is there evidence of induction of an immune response to the vaccine and what impact does an adjuvant (IC31®) have on the immune response – i.e. magnitude and anti-viral phenotype of T cell response.
3. To what extent is the immune response robust and durable?
4. Is there evidence of a pharmaco-dynamic effect of the vaccine indicative of potential efficacy i.e. reduction in serum HBsAg and/or increase in serum antibody to HBsAg; if so is the response dose dependent and is the response modified by inclusion of IC31®?

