### 9.3 Full Analysis Set

The Full Analysis Set comprises all members of the Safety Analysis Set with at least one complete post-vaccination immunogenicity result.

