### 9.4 Immunogenicity Analysis Set

The Immunogenicity Analysis Set comprises all members of the Full Analysis Set with immunogenicity assessments at screening followed by days 1, 8, 29, 36, 57, 64 and 85, a full set of 3 doses of investigational product and with no important protocol deviations adjudicated as relevant by the medical team. Subjects with missing day 1 peripheral blood mononuclear cells (PBMC) may be included if screening PBMC data are available to calculate a baseline. [Section 12.2](#) gives more information about the classification of important protocol deviations.

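### The first-named virology summaries use a set defined by ELISpot completeness and dose completion, neither of which bears on whether an HBsAg, HBV DNA or HBsAb result is valid (minor)

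*SAP*

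**What the plan says.** SAP 12.8 (Virology Analysis) gives summaries of HBsAg and HBV DNA "for all subjects in the Immunogenicity Analysis Set and repeated for the Full Analysis Set if different". HBsAb seroconversion is tabulated "by visit for the Immunogenicity Analysis Set and repeated over the Full Analysis set if different". For the listing, the section states: "Individual subject results for all virology parameters will be listed for the Full Analysis Set".

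Both sets depend on immunogenicity results, which Protocol 3.3.2 and SAP 12.7.1 identify as IFN-gamma ELISpot on PBMC:

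- **Full Analysis Set (SAP 9.3):** dosed subjects "with at least one complete post-vaccination immunogenicity result". The word complete is not defined.
- **Immunogenicity Analysis Set (SAP 9.4):** Full Analysis Set members "with immunogenicity assessments at screening followed by days 1, 8, 29, 36, 57, 64 and 85", plus "a full set of 3 doses of investigational product" and no important deviation judged relevant. Subjects missing the Day 1 PBMC sample "may be included if screening PBMC data are available to calculate a baseline". SAP 8.3 repeats that anyone with fewer than three doses is excluded.

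Appendix 1 of the SAP carries this through: Tables 14.2.2.1 and 14.2.2.2 and Figure 14.2.2.5 use the Immunogenicity Analysis Set. Tables 14.2.2.3 and 14.2.2.4, Figure 14.2.2.6 and Listing 16.2.6.2 use the Full Analysis Set. Table 14.2.2.3 (HBsAg and HBV DNA) is the only virology table marked as top line. No output of post-dose virology uses the Safety Analysis Set or a set defined by virology data.

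**The concern.** Protocol 7.11.3 has virology done on serum or plasma, sent in batches to a separate laboratory. A failed PHA control removes a whole PBMC sample (SAP Appendix 2, step 4), but it says nothing about the HBsAg value from the same visit. Protocol 10.10 assigns the Immunogenicity Analysis Set to immunological variables and leaves the virology analysis to the SAP, so using it for virology is the SAP's own choice.

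Two things are at stake in the Immunogenicity Analysis Set tables.

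- **Precision.** With 10 subjects per arm, each subject lost for a PBMC reason visibly widens the t-based interval that SAP 12.8 plans for HBsAg change.
- **Bias.** Protocol 7.10.1 stops dosing for subjects who reach ALT, INR or bilirubin limits. Protocol 2.1.4 says an effective product would kill infected hepatocytes and could in theory provoke a flare. A subject stopped early on that ground has fewer than three doses and leaves the set, although Protocol 7.10 and 7.10.1 intend virology collection to continue. That exclusion occurs after randomisation and may be related to HBsAg change.

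Virological parameters stand among the secondary endpoints in Protocol 3.3.2. One of the key issues in Protocol 2 is: "Is there evidence of a pharmaco-dynamic effect of the vaccine indicative of potential efficacy". The Day 85 analysis, which includes virology, is meant to inform formulation and dose (Protocol 10.11, SAP 10.2).

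**Working it through.** The study is descriptive and states no power or attrition figure, so there is no figure of the plan's to reproduce. The planned size is consistent: 6 arms × 10 = 60, and the cohort table sums to 5+10+5+5+10+10+5+10 = 60.

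**Inputs**

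- Samples needed for the Immunogenicity Analysis Set: screening plus Days 1, 8, 29, 36, 57, 64 and 85, which is 8, or 7 if Day 1 is waived (SAP 9.4).
- Post-vaccination samples that can qualify a subject for the Full Analysis Set by Day 85: Days 8, 29, 36, 57, 64 and 85, which is 6 (flow chart and SAP 9.3).
- Per-sample PBMC loss rate f: not in the documents. Assumed 1% to 20%, independent between samples.

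**Loss from the Immunogenicity Analysis Set by PBMC failure alone**

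P(excluded) = 1 − (1 − f)^8 with all samples needed, or 1 − (1 − f)^7 with the Day 1 waiver. For example, 1 − 0.95^7 = 1 − 0.698 = 30.2%.

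| f | 8 needed | 7 needed | Left of 10 per arm (7 needed) | Lost of 60 (7 needed) |
|---|---|---|---|---|
| 1% | 7.7% | 6.8% | 9.3 | 4.1 |
| 2% | 14.9% | 13.2% | 8.7 | 7.9 |
| 5% | 33.7% | 30.2% | 7.0 | 18.1 |
| 10% | 57.0% | 52.2% | 4.8 | 31.3 |
| 20% | 83.2% | 79.0% | 2.1 | 47.4 |

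Exclusions for doses or deviations would come on top of these.

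**Effect on the interval for HBsAg change**

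Half-width = t(0.975, n − 1) × SD / √n.

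- n = 10: 2.262 / √10 = 0.715 SD.
- n = 7: 2.447 / √7 = 0.925 SD.
- Ratio 0.925 / 0.715 = 1.29, so the interval is 29% wider at equal SD.

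**Loss from the Full Analysis Set**

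All six post-vaccination samples must fail, so P(excluded) = f^6. The chance that at least one of 60 subjects is lost is 1 − (1 − f^6)^60.

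| f | Per subject | Any of 60 |
|---|---|---|
| 5% | 1.6 × 10⁻⁸ | 9 × 10⁻⁷ |
| 10% | 1.0 × 10⁻⁶ | 6 × 10⁻⁵ |
| 20% | 6.4 × 10⁻⁵ | 0.4% |

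Failures that cluster within a subject or site would raise these figures. So would reading complete to mean both assays, all nine peptides and the peptide mix.

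The first post-dose HBsAg and HBsAb samples are at Day 29, after the Day 8 PBMC draw and alongside another. A subject with post-dose virology but no complete ELISpot result would therefore normally have had at least two PBMC samples missing or failed.

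**The case against.** A reader might infer that virology data are discarded whenever a PBMC sample fails. The documents do not support that. The same summaries are repeated in the Full Analysis Set, which needs one complete post-vaccination result and sets no condition on doses, visits or deviations. Its HBsAg/HBV DNA table carries the top-line mark. The losses of 30% or more and the 29% wider interval belong to the Immunogenicity Analysis Set tables alone. SAP 12.8 names that set first, but does not call it primary for virology.

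A reader might also take HBsAg change to be the only pharmacodynamic signal. The same key issue in Protocol 2 names an increase in antibody to HBsAg as well, and SAP 12.8 tabulates HBsAb.

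There are further fair points. Pairing a per-protocol type of set with a broader one is conventional. SAP 11.3 asks the blinded review to judge whether deviations matter for immunogenicity and virology, so applying the deviation criterion to virology looks deliberate. Virology is not in the stated objectives or in SAP 7.2, and SAP 12.0 treats every endpoint as exploratory without hypothesis tests. If PBMC failure is unrelated to virology, losing those subjects costs precision and does not bias the result.

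Most of this stands, and it is why the point is minor. It does not justify requiring complete ELISpot data for a virology summary. The possible bias comes through the three-dose condition, which does not depend on why PBMC samples fail, and it does not reach the Full Analysis Set tables.

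**Conclusion.** The point holds as a minor one. The first-named virology summaries apply conditions on ELISpot completeness and dose completion that have no bearing on the validity of a virology result. At an assumed independent loss of 1%, 5% or 10% per sample, about 7%, 30% or 52% of subjects would leave those tables. The three-dose condition could also remove subjects in whom treatment had a marked liver effect. The documents give no basis for sizing that bias.

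The Full Analysis Set repeat avoids nearly all of the loss. What remains there is a dosed subject with virology data but no complete post-vaccination ELISpot result, who appears in no virology summary and not in Listing 16.2.6.2. This should be rare.

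The figures assume independent losses at the stated rates, equal SD, and that an assessment in SAP 9.4 means a usable result. If a sample merely has to have been taken, fewer subjects would leave.

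**What to change.** In SAP 12.8, summarise each virology parameter over Safety Analysis Set subjects with a baseline and at least one post-dose value of that parameter. List virology for the whole Safety Analysis Set. Keep the Immunogenicity Analysis Set version and label it supportive.

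In Appendix 1:

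- Tables 14.2.2.3 and 14.2.2.4 and Figure 14.2.2.6 move to the new population. The top-line mark stays on 14.2.2.3.
- Tables 14.2.2.1 and 14.2.2.2 and Figure 14.2.2.5 stay as supportive outputs.
- Listing 16.2.6.2 moves its virology content to the Safety Analysis Set.

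The flow chart schedules HBV DNA only at screening and Day 225, so for that parameter the post-dose condition can normally be met only in the follow-up analysis. It would also help to define complete in SAP 9.3.

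The cost is SAP wording and a change of population flag in programming. No new data, visits or samples are needed, and Protocol 10.3 does not require a protocol amendment for analysis changes. The change should be made before the Day 85 unblinding.

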3.3.2 Secondary endpoints/outcomes

Immunological parameters:

The immunogenicity of Vaccine FP-02.2 will be determined using an IFNy ELISPOT assay. The output for the ELISPOT assay will be number of cells producing interferon gamma (IFN- γ) in response to exposure to native peptides derived from FP-02.2 using an ex vivo and cultured assay. Negative assay controls will contain no peptide and positive controls will use a T cell mitogen.

Additional exploratory immunological assays such as T Cell proliferation assays, intracellular cytokine staining assays, ELISA-based assays to measure FP-02.2-specific antibodies or other suitable assays may be used to further characterise the immune responses to Vaccine FP-02.2. The frequency of regulatory cells, expression of co-stimulatory and inhibitory markers may be measured by flow cytometry.

Immunological data from samples collected within the follow-up phase will be regarded as exploratory, including IFNy ELISPOT data.

Virological parameters:

The following will be measured by means of ELISA-based assays:

- Quantitative HBsAg
- Anti HBsAg antibody
- A validated HBV DNA TaqMan assay will be used to quantitatively measure HBV DNA.

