7.6.2.2 Determination of virological parameters

- Quantitative HBV DNA levels (PCR)
- Quantitative HBsAg levels (ELISA)
- Quantitative HBsAb levels (ELISA)

Immunological (IFNy ELISpot assay) and virological assessments will follow the OECD Principles of GLP.

7.6.3 **Assessment schedule**

Screening Visit

The screening assessment is described in Section 7.2.1.

Randomisation will be performed by IRT up to 3 days prior to first injection to allow data from screening to be available for confirmation of eligibility criteria and for the central pharmacy to supply medication to site.

Visit 1:

The following assessments and procedures will be performed on Day 1:

Pre-vaccination

- Review of eligibility criteria
- Urine pregnancy test in women of childbearing potential
- Blood for CMI
- HBsAg and HBsAb monitoring
- Vital signs
- Physical examination
- Documentation of concomitant medication
- Documentation of AEs
- Vaccination
- Contact IRT for drug supply
- Dispense diary card

Post-vaccination

- Injection site tolerability

- Documentation of concomitant medication
- Documentation of AEs

The subject will be asked to stay in the clinic for at least 4 hours following the first injection.

Visit 2

The following assessments and procedures will be performed on Day 2:

- Vital signs
- Physical examination
- Injection site tolerability
- Documentation of AEs and concomitant medications
- Review diary card for local tolerability

Visit 3

The following assessments will be performed on Day 8:

- Vital signs
- Physical examination
- Injection site tolerability
- Safety laboratory tests
- Documentation of concomitant medication
- Blood for CMI
- Documentation of AEs
- Review diary card for local tolerability
- Dispense new diary cards

Visits 4 and 6 (administration of booster vaccinations)

The following assessments will be performed on Days 29 and 57:

Pre-vaccination

- Urine pregnancy test in women of childbearing potential (pre-vaccination)
- Safety laboratory tests (pre-vaccination)
- Vaccination
- Vital signs
- HBsAg and HBsAb monitoring
- Physical examination
- Documentation of concomitant medication
- Documentation of AEs
- Blood for CMI

Post-vaccination

- Injection site tolerability (post-vaccination)
- Documentation of concomitant medication
- Documentation of AEs
- Dispense diary card

The subject will be asked to stay in the clinic for 2 hours after each booster vaccination.

Telephone Contact 24 hours after booster vaccinations

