10.3 Statistical analysis plan

The proposed statistical analyses for this study will be detailed in a separate statistical analysis plan (SAP), which will be finalised prior to database lock. Any changes to the statistical analysis described in this protocol do not require a protocol amendment but must be described as a 'change to the protocol planned statistical analysis' in the SAP and the clinical study report.

The statistical analysis and report will conform to the relevant ICH requirements.

Data listings and summary tables will be generated using the software SAS® Version 9.3 or later. All data recorded in the eCRFs will be included in data listings. The SAS datasets and programs will be made available to the Sponsor at study closure.

Summary tables and data listings will be presented by treatment arm and time point.

The standard summary statistics for continuous variables will comprise number of valid observations, arithmetic mean, standard deviation, median, quartiles, minimum, and maximum. The geometric mean and coefficient of variation will also be presented for continuous variables which are positive and substantively positively skewed (such as liver enzyme levels, ELISpot counts and measures of viral load). The standard summary statistics for categorical data will comprise absolute and relative frequencies (proportions).

If continuous variables are assessed both at and after baseline, change from baseline will be calculated and summarised. If categorical variables are assessed both at and after baseline, then cross-tabulations will be presented by category at baseline.

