Table 14.2.2.2	Qualitative Virology Results by Time Point - HBsAb	Immunogenicity Analysis Set	
Table 14.2.2.3	Quantitative Virology Results by Time Point - HBsAg and HBV DNA	Full Analysis Set	X
Table 14.2.2.4	Qualitative Virology Results by Time Point - HBsAb	Full Analysis Set	
Figure 14.2.2.5	Line Plot of Change from Baseline in log10 HBsAg at each Timepoint by Treatment Group	Immunogenicity Analysis Set	
Figure 14.2.2.6	Line Plot of Change from Baseline in log10 HBsAg at each Timepoint by Treatment Group	Full Analysis Set	
Table 14.3.1.1	Summary of Investigational Product Exposure	Safety Analysis Set	
Table 14.3.2.1	Overall Summary of Adverse Events	Safety Analysis Set	
Table 14.3.2.2	Treatment-emergent Adverse Events by System Organ Class and Preferred Term	Safety Analysis Set	X
Table 14.3.2.3	Treatment-emergent Adverse Events by System Organ Class and Maximum Severity	Safety Analysis Set	
Table 14.3.2.4	Serious Adverse Events by System Organ Class and Preferred Term	Safety Analysis Set	
Table 14.3.2.5	Possibly Treatment-Related Treatment-emergent Adverse Events by System Organ Class and Preferred Term	Safety Analysis Set	
Table 14.3.2.6	Serious Possibly Treatment-Related Adverse Events by System Organ Class and Preferred Term	Safety Analysis Set	
Table 14.3.2.7	Possibly Treatment-Related Treatment-emergent Adverse Events by System Organ Class and Maximum Severity	Safety Analysis Set	
Table 14.3.2.8	Treatment-emergent Adverse Events leading to Discontinuation of Investigational Product by System Organ Class and Preferred Term	Safety Analysis Set	
Table 14.3.2.9	Adverse Events with Fatal Outcome by System Organ Class and Preferred Term	Safety Analysis Set	
Table 14.3.2.10	Adverse Events of Special Interest by System Organ Class and Preferred Term	Safety Analysis Set	
Table 14.3.3.1.1	Haematology Results by Time Point	Safety Analysis Set	
Table 14.3.3.1.2	Investigator Assessed Clinically Significant Postbaseline Haematology Results	Safety Analysis Set	
Table 14.3.3.1.3	Shift Summary of Haematology Results by Reference Range and Time Point	Safety Analysis Set	

Table 14.3.3.2.1	Biochemistry Results by Time Point	Safety Analysis Set	
Table 14.3.3.2.2	Investigator Assessed Clinically Significant Postbaseline Biochemistry Results	Safety Analysis Set	
Table 14.3.3.2.3	Shift Summary of Biochemistry Results by Reference Range and Time Point	Safety Analysis Set	X
Table 14.3.3.3.1	Quantitative Urinalysis Results by Time Point	Safety Analysis Set	

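### SAP 12.8 summarises HBsAb only as above or below 10 mIU/mL, so no planned table or figure gives an arm-level change in titre

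*SAP*

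**What the plan says.** **Protocol.** Section 7.6.2.2 lists "Quantitative HBsAb levels (ELISA" among the virological determinations. Section 3.3.2 places "Anti HBsAg antibody" among the virological parameters under the secondary endpoints. Table 1 schedules it at screening and on Days 1, 29, 57, 85 and 225, and Table 6 counts six virology samples. Key issue 4 in section 2 asks about "reduction in serum HBsAg and/or increase in serum antibody to HBsAg; if so is the response dose dependent" and whether IC31 modifies the response. For a continuous variable assessed at and after baseline, section 10.3 says "change from baseline will be calculated and summarised". For a categorical one it requires cross-tabulation by baseline category. It also requires changes to the planned analysis to be described in the SAP and the study report.

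**SAP.** Section 12.8 states: "The antibody to hepatitis B surface antigen (HBsAb) will be summarised by 'seroconverted' or 'not seroconverted' by visit". The cut-off follows: "Seroconversion corresponds to HBsAb > 10 mIU/mL". The only HBsAb tables in Appendix 1 are 14.2.2.2 and 14.2.2.4, each titled "Qualitative Virology Results by Time Point - HBsAb". By contrast, HBsAg gets descriptive statistics on the log10 scale, change from baseline with SE and 95% CI, and a line plot by treatment group. Individual results for all virology parameters are to be listed for the Full Analysis Set (Listing 16.2.6.2). Section 4.1 declares two changes from the protocol, one on physical examination and one on the Immunogenicity Analysis Set. The handling of HBsAb is not among them.

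**The concern.** Key issue 4 asks about an increase and its relation to dose. A single cut-off registers an increase only when a subject crosses it. A rise from 1 to 9 mIU/mL, or from 15 to 500 mIU/mL, leaves the subject in the same category, so every planned summary shows no change.

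HBsAg and HBsAb are the two halves of the same question, yet only HBsAg is summarised as a quantity. SAP 10.2 says the primary analysis is needed to confirm the formulation and dose for the next study, so a graded antibody response by arm is relevant to that decision. Sponsor and CRO staff are unblinded at that analysis. A titre summary first specified afterwards would be post hoc.

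**Working it through.** **Is there a figure to reproduce?** No. The documents give no power, SD, baseline level, expected rise or LLOQ for HBsAb. The planned arms sum to 5+10+5+5+10+10+5+10 = 60, which is 10 per arm once placebo and IC31-only subjects are pooled across cohorts. Everything below uses n = 10. The other inputs are assumptions that show direction and rough size.

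**Protocol 10.3 against SAP 12.8.**

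| If HBsAb is treated as | Protocol 10.3 requires | Planned in SAP 12.8? |
|---|---|---|
| continuous | summary and change from baseline | no |
| categorical | cross-tabulation by baseline category | no |

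The gap exists on either reading, and SAP 4.1 does not mention it.

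**Precision of the yes/no table at n = 10 (exact 95% CI).** 0/10: 0 to 30.8%. 1/10: 0.3% to 44.5%. 2/10: 2.5% to 55.6%. As a yardstick only, since no tests are planned, Fisher's exact p is 0.087 for 0/10 against 4/10 and 0.033 for 0/10 against 5/10.

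**Precision of a titre summary.** Let SD be the standard deviation of change in log10 HBsAb, assumed to lie between 0.3 and 0.7.

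- Within one arm, half-width = t(0.975, 9) × SD/√10, with t = 2.262.
- Between two arms, half-width = t(0.975, 18) × SD × √(2/10), with t = 2.101.

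| SD | within arm | between arms | between arms, as a fold difference |
|---|---|---|---|
| 0.3 | 0.21 | 0.28 | 1.9 |
| 0.5 | 0.36 | 0.47 | 3.0 |
| 0.7 | 0.50 | 0.66 | 4.5 |

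An observed threefold rise is log10(3) = 0.48. Its within-arm CI would exclude zero at SD 0.3 and 0.5, but not at 0.7.

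**The same threefold rise in the yes/no table.** Assume log10 titre is normal with SD 0.5 at both visits, and baseline geometric mean is 1 to 3 mIU/mL. The expected number above 10 mIU/mL is 10 × P(Z > (1 − mean log10)/0.5).

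- Geometric mean 1 rising to 3: z goes from 2.00 to 1.05, and the count from 0.2 to 1.5 of 10.
- Geometric mean 3 rising to 9: z goes from 1.05 to 0.09, and the count from 1.5 to 4.6 of 10.

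**Two arms compared by simulation.** The comparison used 4,000 runs, 10 per arm, two-sided 0.05, baseline SD 0.4, change SD 0.4, and mean baseline log10 of −0.5, 0 or 0.5 (about 0.3, 1 and 3 mIU/mL). It set a t-test on change in log10 titre against Fisher's test on the cut-off.

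| Mean rise (log10) | t-test on change | Fisher's test on >10 mIU/mL |
|---|---|---|
| 0.3 | 35% to 37% | 0% to 5% |
| 0.5 | about 75% | 0% to 16% |
| 1.0 | about 100% | 3% to 68% |

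None of these calculations includes values below LLOQ. If many values fall there, substitution of LLOQ/2 (SAP 14.1) makes them nearly constant and the advantage of the quantitative summary shrinks.

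**The case against.** **The endpoint analysis was left to the SAP.** Protocol 10.10 says the planned analysis of each virological endpoint will be set out there, and the examples of skewed variables in 10.3 do not name HBsAb. That gives the SAP room to choose a method. It does not remove the requirement in 10.3 to describe a change, and the yes/no choice does not meet the rule for categorical variables either.

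**HBsAb is a minor variable in a descriptive study.** In protocol 3.3.2 only HBsAg is labelled quantitative. The SAP's only secondary variable is T-cell immunity, and SAP 12.0 treats all endpoints as exploratory with no hypothesis testing. This is right and limits the severity. The proposed addition is descriptive too.

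**The yes/no table has a purpose.** The placebo arm is there partly to show the natural seroconversion rate, which is a proportion. That is a good reason to keep the table, but not to omit the titre.

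**The trial can still show a rise.** A reader might infer from SAP 12.8 that the trial cannot show an antibody increase or dose dependence. The documents do not support that. The values are collected at six visits and individual results are to be listed; numeric values are the natural reading, though the SAP does not say so. Protocol 10.3 presents summaries by arm, so seroconversion proportions give a coarse comparison across doses. Key issue 4 is also worded as and/or, and its HBsAg half is analysed quantitatively. What is missing is an arm-level estimate of titre change with an interval.

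**The fix would not settle dose dependence.** This also stands. The within-arm interval does not compare doses, and the between-arm half-width at SD 0.5 is about threefold. SAP 12.7.2 does not fill the gap: it allows optional exploratory analyses of immunogenicity data only.

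**Conclusion.** The point holds as a gap in the planned summaries and an undeclared departure from protocol 10.3. It does not mean that data are lost or that key issue 4 cannot be answered. No planned table or figure will show how far HBsAb titre moved in any arm, and changes that stay on one side of 10 mIU/mL will appear only in a subject listing.

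The size of the loss cannot be fixed from the documents, because titre SD, baseline level, LLOQ and the share of values below it are not given. Under the assumed ranges, a threefold rise is visible within an arm on the log scale at an SD up to about 0.5, while the yes/no count moves by roughly one to three subjects in 10. Between doses, even the quantitative summary resolves only differences of about threefold or more at that SD. Arms smaller than 10 in the Immunogenicity Analysis Set would widen every interval. This is a worthwhile, nearly free improvement to a descriptive analysis.

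**What to change.** Before database lock, while the SAP is still open for finalisation at the blinded data review (SAP 11.3):

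- Add HBsAb to Tables 14.2.2.1 and 14.2.2.3 by treatment group and visit, in log10 mIU/mL, with geometric mean, median, quartiles, and change from baseline with SE and 95% CI.
- Set values below LLOQ to LLOQ/2, as SAP 14.1 already provides, and report the number below LLOQ in each cell so that a near-constant column is not over-read.
- Keep the seroconversion tables alongside.
- State that Listing 16.2.6.2 shows the numeric HBsAb value.
- If the sponsor prefers the yes/no summary alone, declare that in SAP 4.1 and add the cross-tabulation by baseline category that protocol 10.3 requires.

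The cost is a few lines of SAP text and one more parameter in two existing tables. No new samples, visits or assays are needed.
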